#### 3.4.8 Lost to follow-up

Registry pregnancy reports will be considered complete for live births when data regarding the pregnancy, neonatal and infant outcomes through one year have been received. For pregnancies that do not result in a live birth, follow-up is complete once pregnancy outcome details have been provided.

At enrollment (and as part of the informed consent process), patients will be asked to provide their contact details as well as the contact details of at least two other people (e.g., a family member or a friend living outside of the patient's home), in case the patient is not reachable and an alternate contact is needed. Patients will be contacted by email (if provided), then by telephone. If the patient cannot be reached by these modalities, then the alternate contact(s) will be contacted by the registry site.

For registry purposes, patients will be considered lost to follow-up if any time-based assessment is missed and the corresponding data have not been received by the registry after making additional follow-up attempts using all contact modalities available (e.g., phone, fax, registered receipt letter). At least 3 attempts will be made up to 4 months after the expected date of the missed assessment. Patients will be considered lost to follow-up 30 days after the last contact attempt. The case will be re-opened should additional information be later obtained. All HCPs on record will be contacted prior to considering the patient lost to follow-up. All data collected prior to considering the patient lost to follow-up will be used for analysis and reporting purposes, to the extent possible. The date of discontinuation is considered the date of the last successful contact with the patient.

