#### 3.1.2 Patient withdrawal and discontinuation from registry

Patients may withdraw consent provided at enrollment and discontinue participation in the registry at any time, with no effect on their medical care or access to treatment. If a patient withdraws from registry participation, any known reason for withdrawal is to be documented in the database. All information already collected as part of the registry will be retained for analysis; however, no further efforts will be made to obtain or record additional information regarding the patient for the purpose of this registry.

Patients will be considered prematurely discontinued from the registry in the following cases:

- the patient has specifically requested to withdraw from the registry
- the patient is lost to follow-up
- the patient died

For live births, premature discontinuation from the registry is considered in the following cases:

- the mother has specifically requested to withdraw her infant from the registry
- the mother is lost to follow-up
- the mother died
- the infant died

Data to be collected at the end of patient participation will include all pregnancy and infant outcome follow-up data available at the time of discontinuation, as well as the reason for discontinuation.

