#### 3.4.3 Post-partum (up to 3 months after expected delivery date)

At the time of the estimated delivery the patient's registry site will be contacted by the registry team and asked to provide the necessary follow-up information. Although it is anticipated that data regarding pregnancy outcome will be provided by an obstetrician or other perinatal HCP, it may also be provided by the patient's neurologist, the patient herself or other physician if necessary. The patient's primary HCP may change during the course of follow-up and data may be collected from multiple sources. In order to prevent loss to follow-up and incomplete reports, alternative sources of information will be pursued as required, if contact information is available. As with all other time points, no direct patient identifiable information such as name and address will be reported to the registry. Baseline information and outcome as well as other follow-up assessment will be linked using the unique patient ID.

The following data will be collected post-partum:

- Documentation of informed consent for the infant.
- Date of contact, contact information (separate database) and specialty of HCP(s) providing information.
- Pregnancy outcome (term or preterm live birth, elective termination, fetal death).
- Date of pregnancy outcome or gestational age in weeks.
- If elective termination, specify primary reason (identified anomaly, increased risk of anomaly, non-medical reasons).
- Obstetric and delivery complications (preterm delivery, premature rupture of membranes (PROM), preeclampsia/severe pregnancy-induced hypertension (PIH)/proteinuria, gestational diabetes, intrauterine growth retardation (IUGR) and so on).
- Live births: whether single or multiple births (if multiple, number of fetuses).
- For each infant:
  - 1. Infant gender
  - 2. Birth length (in or cm)
  - 3. Gestational age (weeks, days)
  - 4. Birth weight (lbs/oz or grams)
  - 5. Head circumference (in or cm)
  - 6. Apgar scores (1, 5 and 10 minutes)
- Tests/procedures performed and any associated diagnoses.
- Infant vital status (alive / deceased).
- Presence of major congenital malformations, e.g., heart defect, spina bifida, club foot deformity, cleft palate.
- Presence of minor congenital malformations (i.e., anomalies with no serious medical or cosmetic consequence to the infant).

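### Any one unrecovered assessment, including an interim form, triggers loss to follow-up and can discontinue mother and infant before the outcome or one-year data are due

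*Protocol*

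**What the plan says.** Section 3.4.8 sets the rule: "patients will be considered lost to follow-up if any time-based assessment is missed and the corresponding data have not been received by the registry". The same sentence limits this to the situation "after making additional follow-up attempts using all contact modalities available (e.g., phone, fax, registered receipt letter". Three conditions follow:

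- "At least 3 attempts will be made up to 4 months after the expected date of the missed assessment".
- "All HCPs on record will be contacted prior to considering the patient lost to follow-up".
- "Patients will be considered lost to follow-up 30 days after the last contact attempt".

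Data gathered before that point are kept for analysis, and "The case will be re-opened should additional information be later obtained". The discontinuation date is set back to the last successful contact.

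Section 3.4 lists the time-based assessments. The mid-second-trimester and 3-month forms are among them, next to the post-partum and one-year forms.

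Section 3.1.2 says "Patients will be considered prematurely discontinued from the registry in the following cases" and lists loss to follow-up among them. For live births, loss of the mother discontinues the infant as well. The section treats discontinuation as the end of participation, as do the schedule tables. Under Section 3.4.6, an infant without a completed one-year assessment has those data collected when it is discontinued.

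Two other statements bear on the point. Section 3.4.8 opens by defining a complete report by outcome: through one year for a live birth, and by pregnancy outcome details otherwise. Section 3.4.3 says that around the estimated delivery the patient's registry "site will be contacted by the registry team and asked to provide the necessary follow-up information".

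**The concern.** The trigger does not distinguish a form that carries an outcome from one that does not. A woman whose mid-trimester form is never recovered gets the same status as one whose pregnancy outcome is never learned, although her outcome may still be obtainable. This does not match the outcome-based definition of completeness in the same section.

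Three things are at stake.

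- **Primary analysis.** Section 5.1 restricts it to prospectively identified cases with outcome information. A pregnancy discontinued on an interim form and not pursued afterwards drops out of that set.
- **Infant data.** The Executive summary and Section 3.4.5 count on malformations found up to one year, and a secondary objective concerns infants at about one year. If an infant is discontinued early, Section 3.4.6 would have its one-year data collected at that earlier age.
- **Registry continuation.** Section 3.4.9 names a high rate of loss to follow-up as a possible reason to stop. A rule that counts interim gaps as losses raises that rate without showing that outcomes are unobtainable.

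**Working it through.** **Power figure in the plan.** Section 5.2 claims more than 80% power with 500 women, 3% background, an 80% increase (5.4%) and two-sided α of 0.05. A one-sample normal approximation gives

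Φ{[(0.054 − 0.03)·√500 − 1.96·√(0.03·0.97)] / √(0.054·0.946)} = Φ{(0.5367 − 0.3344)/0.2260} = Φ(0.895) = 81.5%.

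The figure reproduces. By the same formula, 80% needs at least 478 women with outcomes, which leaves 500 − 478 = 22 (4.4%) to spare. Section 5.2 states no allowance for loss. For illustration only, with loss from any cause:

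| Loss | Women with outcomes | Power |
|---|---|---|
| 5% | 475 | 79.8% |
| 10% | 450 | 78.0% |
| 20% | 400 | 74.0% |

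An exact binomial test at 500 gives 75.1%, so the margin also depends on the method.

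**Calendar inputs.**
- Mid-trimester form: 21 weeks ± 2 (Section 3.4.2).
- Post-partum window: to 3 months after the estimated date of delivery (EDD) (Section 3.4).
- 3-month window: EDD + 3 months to infant age 9 months; one-year window: 10 to 14 months (Section 3.4).
- Attempts: at least three, up to 4 months after the expected date, with no minimum spacing; then 30 days (Section 3.4.8).
- Assumptions: EDD at 40 weeks, birth at EDD, one month = 30.44 days = 4.35 weeks. The expected date within a window is not defined, so ranges are shown.

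**Mid-trimester form unrecovered.**
- Latest status: 21 + 4 × 4.35 + 30/7 = 42.7 weeks (40.7 to 44.7 for due dates of 19 to 23 weeks).
- Earliest status, with all attempts made at once: 21 + 30/7 = 25.3 weeks (23.3 to 27.3).
- Post-partum window closes: 40 + 3 × 4.35 = 53.0 weeks.

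The status always falls before the post-partum window closes. It falls before delivery at week 40 only if the last attempt is made before 40 − 30/7 = 35.7 weeks, that is, within 14.7 weeks (about 3.4 months) of week 21.

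**3-month form unrecovered.**
- Expected at 3 months: 3 + 1 = 4 months at the earliest, 3 + 4 + 1 = 8 months at the latest. Both precede the opening of the one-year window at 10 months.
- Expected at 9 months: 9 + 1 = 10 months to 9 + 4 + 1 = 14 months, which is inside the one-year window.

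**What happens after the status.** Section 3.1.2 rules out further efforts only when consent is withdrawn. Section 3.4.8 re-opens a case if information arrives. Section 3.4.6 calls for a discontinuation collection. None of them says that the post-partum or one-year assessment is still actively sought from a woman already classed as lost.

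**The case against.** The strongest reply is that the rule is well guarded. A reader of the trigger alone might infer that one missed form makes a woman lost. The text does not support that: attempts by all available routes, contact with all HCPs and a 30-day wait come first. A reader might also infer that a silent site is enough. That is not supported either: Section 3.4.8 provides for contact with the patient and her alternate contacts, and Sections 3.4 and 6.2 allow data to be taken from the mother where local rules permit.

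A direct contradiction with Section 3.4.3 is also tempting, but not shown. If attempts run the full 4 months, the contact at delivery comes first, and nothing in Section 3.4.8 cancels it. The tension arises only when attempts finish early.

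Other points lessen the effect:

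- Women enrolled after week 19 have no mid-trimester form (Section 3.4.2).
- A birth outcome recorded post-partum stays in the analysis if the 3-month form is later missed.
- Section 3 plans a contact about six months after birth, where allowed, to limit loss.
- The discontinuation collection covers pregnancy outcome and malformations, although it cannot record events that have not yet happened.

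All of this stands, and it narrows the point. It does not remove the mismatch between an any-form trigger and an outcome-based definition of completeness, or supply a statement that later assessments are still pursued.

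**Conclusion.** The point holds as a badly placed trigger. Loss to follow-up depends on any one unrecovered time-based assessment, and it discontinues mother and infant. On the protocol's own windows this can happen at about week 25.3 to 42.7, against a post-partum window that closes at about week 53. For infants it can happen at 4 to 8 months, before the one-year window, or at 10 to 14 months, depending on how the undefined expected date is read. The timing rests on the stated assumptions about EDD, birth date and month length.

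A reader might conclude that follow-up definitely ends at this status, or that a given share of outcomes is lost. The documents support neither. Cases can be re-opened, earlier data are kept, and no loss rate or missed-form rate is given, so the number of outcomes forgone cannot be stated. The power figures show only that the planned size has little slack; they do not measure the effect of this rule. What can be said is that the text permits a case to lapse on an interim form, with re-opening that depends on information arriving rather than on being sought.

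**What to change.** In Section 3.4.8, declare loss to follow-up only when the pregnancy outcome or, for a live birth, the one-year assessment is still missing after all attempts. This matches the section's own definition of a complete report. Record an unrecovered mid-trimester or 3-month form as a missed assessment. State that contact continues at each later scheduled time point unless consent is withdrawn, and define the expected date for each assessment window.

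Then reconcile Sections 3.1.2, 3.4.3, 3.4.6 and 3.4.8, so that discontinuation of mother and infant, the contact at delivery and the collection of one-year data follow the same rule. The discontinuation date, now the last successful contact, should also fit with re-opened cases.

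The cost is about one paragraph of text with matching edits, and a few more contact attempts by existing staff.

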#### 3.4.9 Study discontinuation

Upon agreement with relevant health authorities, Novartis has the right to prematurely terminate this registry at any time. The potential reasons to discontinue this pregnancy registry include, but are not limited to:

- Accumulation of sufficient information to meet the registry's scientific objectives.
- Feasibility [e.g., low prevalence of exposure, poor enrollment (due to patient or physician inability to participate), high rate of loss to follow-up].
- Availability of alternative sources of data suitable to meet the scientific objectives.

### 3.5 Comparison groups

The findings in the proposed pregnancy exposure registry will be compared to external comparison groups, e.g., data collected by external investigators including data made

available from other registries that include pregnancy exposure and outcome information. External comparison groups will include the general surveillance systems such as the National Center on Birth Defects and Developmental Disabilities, U.S. Centers for Disease Control (CDC), or the National Birth Defect Prevention Network, EUROCAT and possibly other national surveillance groups.

The CDC's Metropolitan Atlanta Congenital Defects Program (MACDP) is a population-based birth defect surveillance system that monitors all major birth defects in five counties of the metropolitan Atlanta area (Clayton, Cobb, DeKalb, Fulton, and Gwinnett) with approximately 50,000 annual births from a population of about 2.9 million. MACDP, which started in 1967, acts as the model for many state-based programs and as a resource for the development of uniform methods and approaches to birth defect surveillance, and will be used as the comparator for U.S. based cases. The MACDP uses a 6-digit coding system for birth defect data that is based on an ICD-9 derived system established by the British Pediatric Association. Therefore the data remains compatible with hospital and other data sets, while providing additional specificity for most birth defect codes, thereby facilitating the use of the MACDP as a valid external comparator.

European surveillance of congenital anomalies (EUROCAT) is a European network containing data from population-based registries for the epidemiologic surveillance of congenital anomalies, and will be used as the external comparator group for European cases. EUROCAT, which started in 1979, includes 43 registries from 20 countries covering 29% of the European birth population with 1.5 million births surveyed per year.

There is currently no evidence that MS itself is associated with an increased risk of adverse pregnancy outcomes (i.e., miscarriage, stillbirth or congenital malformations, details see Dahl et al (2005), Dahl (2008), Dahl et al (2008), Kelly et al (2009) and Houtchens (2007), therefore comparison data from large surveillance systems or national statistics should allow a valid comparison. Furthermore, as the highest risk for major malformation is related to exposure during the first trimester, the frequency of congenital malformations among women with first trimester exposure will be compared to women with second and third trimester exposure (if sufficient data are available) to allow an additional internal comparison. Relevant published data sources will be used to evaluate the frequency of other adverse pregnancy outcomes in the exposed population.

## 4 Safety

#### 4.1 Adverse events

An adverse event is the appearance or worsening of any undesirable sign, symptom, or medical condition occurring after signing the informed consent even if the event is not considered to be related to fingolimod. Medical conditions/diseases present before signing the informed consent are only considered adverse events if they worsen after signing the informed consent. Abnormal laboratory values or test results constitute adverse events only if they induce clinical signs or symptoms, are considered clinically significant, or require therapy.

The occurrence of adverse events should be sought by non-directive questioning of the patient at each encounter with the patient. Adverse events also may be detected when they are

volunteered by the patient during or between visits or through routine physical examination, laboratory test, or other assessments. All adverse events must be recorded on the Adverse Events CRF with the following information:

- 1. Severity grade [mild, moderate or severe]
- 2. Relationship to fingolimod (suspected/not suspected)
- 3. Duration (start and end dates or if continuing)
- 4. Whether it constitutes a serious adverse event (SAE)

#### An SAE is defined as an event which:

- is fatal or life-threatening,
- results in persistent or significant disability/incapacity,
- constitutes a congenital anomaly/birth defect,
- requires inpatient hospitalization or prolongation of existing hospitalization, unless hospitalization is for:
  - Routine treatment or monitoring of the studied indication which is not associated with any deterioration in condition.
  - Elective or pre-planned treatment for a pre-existing condition that is unrelated to the indication under study and has not worsened since the start of registry participation.
  - Treatment on an emergency outpatient basis for an event not fulfilling any of the definitions of a SAE given above and not resulting in hospital admission.
  - Social reasons and respite care in the absence of any deterioration in the patient's general condition, or
- is medically significant, i.e. defined as an event that jeopardizes the patient or may require medical or surgical intervention to prevent one of the outcomes listed above.

## Unlike routine safety assessments, SAEs are monitored continuously and have special reporting requirements; see Section 4.2

All adverse events should be treated appropriately. Treatment may include one or more of the following: no action taken (i.e. further observation only); fingolimod dosage adjusted/temporarily interrupted; fingolimod permanently discontinued due to this adverse event; concomitant medication given; non-drug therapy given; patient hospitalized/patient's hospitalization prolonged. The action taken to treat the adverse event should be recorded on the Adverse Event CRF.

Once an adverse event is detected, it should be followed until its resolution or until it is judged to be permanent, and assessment should be made of any changes in severity, the suspected relationship to fingolimod, the interventions required to treat the adverse event, and the outcome.

Information about common side effects already known about fingolimod can be found in the most updated local product label. This information should be discussed with the patient as needed during the informed consent process.

## 4.2 Serious adverse event reporting

To ensure patient safety, every SAE, regardless of suspected causality, occurring after the patient has provided informed consent and until 30 days after the patient has stopped registry participation must be reported to Novartis within 24 hours of learning of its occurrence.

Any SAEs experienced after this 30 day period should only be reported according to the reporter's normal practices for post-marketed adverse event reporting.

Recurrent episodes, complications, or progression of the initial SAE must be reported as follow-up to the original episode, regardless of when the event occurs. This report must be submitted within 24 hours of the investigator receiving the follow-up information. An SAE that is considered completely unrelated to a previously reported one should be reported separately as a new event.

Information about all SAEs is collected and recorded on the Serious Adverse Event Report Form. The investigator must assess the relationship of any SAE to fingolimod, complete the SAE Report Form in English, and send the completed, signed form by fax within 24 hours to the local Novartis Drug Safety and Epidemiology Department. The telephone and telecopy number of the contact persons in the local department of Clinical Safety and Epidemiology, specific to the site, are listed in the investigator folder provided to each site. The original copy of the SAE Report Form and the fax confirmation sheet must be kept with the case report form documentation at the study site.

Follow-up information is sent to the same department to which the original SAE Report Form was sent, using a new SAE Report Form stating that this is a follow-up to the previously reported SAE and giving the date of the original report. The follow-up information should describe whether the event has resolved or continues, if and how it was treated, and whether the patient continued or withdrew from registry participation.

If the SAE is not previously documented in the Package Insert (new occurrence) and is thought to be related to fingolimod, a Drug Safety and Epidemiology Department associate may urgently require further information from the investigator for Health Authority reporting.

#### 4.3 Pregnancies

In some countries (e.g European Union, Japan, Russia, Switzerland), fingolimod is contraindicated in the use relating to pregnancy. Latest local fingolimod product information and educational material for these countries should be referred to for guidance and more information.

To ensure patient safety, each pregnancy in a patient exposed to fingolimod must be reported to Novartis within 24 hours of learning of its occurrence. The pregnancy should be followed up to determine outcome, including spontaneous or voluntary termination, details of the birth, and the presence or absence of any birth defects, congenital abnormalities, or maternal and/or newborn complications.

If physicians are aware of any pregnant patient they should try to enroll the patient and contact the CRO. If the physician's site is already set up and the patient has given written informed consent, data for this new patient can be directly entered into the registry database.

If the CRO becomes aware of a pregnancy they will report the pregnancy to Novartis within 24 hours. When the patient is enrolled in the registry follow up is done through the CRO and the local Novartis safety desk is informed by the CRO about any updates on the case.

If maternal exposed pregnancy information is reported to Novartis directly, the reporter's will be asked to participate in the registry and if possible the call will be immediately transferred to the registry call center for follow-up. Prior to the call transfer, Novartis will collect contact information and basic pregnancy status information in case the call is lost in transfer. In the event the call cannot be transferred, the Novartis' Drug Safety & Epidemiology department should forward the reporter contact information to the CRO registry staff only if and after the reporter has provided their verbal consent, in accordance with local law and regulations.

